9.4.2 Switching

A therapeutic switch will be defined as a subsequent filling of a prescription for an alternative anticoagulant (LMWH, any NOAC, VKA).

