Venous thromboembolism (VTE), including pulmonary embolism (PE) and deep vein thrombosis (DVT), is a leading cause of morbidity and death for cancer patients. Approximately 20% of all VTE cases occur in patients with cancer and more than 20% of patients with cancer will experience VTE (1). There is some evidence that that patients with both cancer and VTE were at a four times increased risk of developing recurrent thromboembolic complications and twice as likely to develop major bleeding during anticoagulant (AC) treatment than those without cancer. This risk varies during the course of the disease with the highest risk immediately after the initiation of chemotherapy (2). Risk factors for developing VTE in cancer patients is multifold and is determined by patient-related, tumor-related, cancer treatment - related and biomarker-related factors. Hence, the population of cancer patients as well as the choice of cancer treatment is highly heterogeneous (3); patients' individual responses to cancer treatment are highly variable often prompting physicians to make tailored decisions regarding the choice of an anticoagulant and the duration of therapy.

Low-molecular-weight heparin (LMWH) is the standard initial treatment for cancer-associated VTE (CAT) (4). For long term treatment, a vitamin K antagonist (VKA), warfarin, is the recommended treatment for several types of cancer including prostate, lung and breast cancers (5). More recently, the role of non-vitamin K oral anticoagulant agents (NOACs) is being assessed in several clinical trials. As the risk of thrombotic event depends on the 'cancer activity' that is variable in different

cancers, no reliable data are available on the risk-benefit balance of the anticoagulation therapy extended beyond 6 months in cancer patients.

An increasing success of cancer treatments results in significant extension of survival, even in cases of metastatic diseases; therefore prevention of debilitating thrombotic events in these patients is gaining importance. Although prostate cancer (PCa) belongs to the cancer types with a relatively low risk of VTE, the burden of patients with PCa is high; thus adequate treatment and secondary prophylaxis of VTE in this population is of clinical and public health importance.

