The outcome of interest is therapy with anticoagulants dispensed from pharmacies (no information is available on drugs delivered in- hospital), hence the analysis focuses on anticoagulant therapies for which an out-patient prescription has been filled, i.e. long-term therapy. A full list of the treatments with their relative ATC codes is found in Annex 3. The anticoagulation treatments that will be assessed include:

1. LMWH (after hospital discharge, long-term use)
2. VKAs
3. NOACs

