9.4 Follow up

9.4.1 Exposure to anticoagulants

The exposure to AC treatment will be defined in two ways:

- the first is by following the patients until the end of the follow-up time, regardless if they are still on the drug or not.
- the second way is to follow up the patients until the filled prescription for each respective drug expires (“on/treatment”).

A grace period of 90 days will be used to define a new prescription of anticoagulant. The duration of a prescription will be derived from the median number of days between consecutive respective prescriptions after the grace period has passed.

The treatment exposure can then be used to study the switching of treatments and the discontinuation of treatments.

A start date will be defined as the date of the dispensed prescription for patients receiving anticoagulation.

Patients will be censored at earliest date of:

- Time of first occurrence of a recurrent VTE event or a bleeding event (major bleeding event i.e. intracranial, gastrointestinal, urogenital bleeding, or other bleeding leading to hospitalisation) or death
 - Patients will be followed until occurrence of one of the above mentioned outcomes of interest; similarly, the analysis is repeated in the same way for the other outcomes of interest. Therefore, the patients were not censored at the first outcome of interest and outcomes on treatment after the first is also taken in to account. Only first-time events of the same type are considered.
- End of observation time (data lock point for the database at 31st October 2017)
- Treatment discontinuation
- Treatment switching patients who switched will be censored at the time of the date of a filled prescription from a pharmacy of the new drug.

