9.4.3 Discontinuation

It will not possible to determine exactly when an anticoagulant drug was discontinued from dispensing data, except when a switch was made, where the date for dispensing of the other drug was considered to mark the end of the exposure to the study drug.

Therefore, two fundamentally different methods will be used to approximate the time when exposure to the anticoagulant drug ended: a dispensed quantity based-method and a method based on refill intervals, which have both been evaluated in a previous study (9).

The dispensed quantity method counts the number of days the dispensed quantity of the drug would last if taken as prescribed and without missed doses. As the dosing of SOC varies greatly over time and between individuals, and the dosage is not recorded in the registers, this method could only be used for NOACs.

The refill interval method counts all days between two dispensings as days on treatment. If there is a gap exceeding six months, a single prescription or no more refills, treatment will be considered to have ceased three months after the last recorded dispensing. If there is another refill after more than six months, another treatment period will be considered to have started.

For both methods, the number of days on treatment days will be added up and a medicine possession ratio (MPR) calculated as the proportion of days on treatment out of the total number of days at risk (time to end of follow up, death or emigration). As a further sensitivity analysis, both methods will be assessed assuming that all patients were fully compliant to treatment (MPR 100%) and allowing

for patient's forgetfulness that every tenth dose is missed (on average). In this case a dispensed quantity would last approximately 11% longer than with full compliance.

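### Protocol 9.4.1–9.4.3 count a pharmacy-dispensed LMWH start followed by a planned VKA as short LMWH therapy plus a switch, although 9.3.2 intends the LMWH class to mean long-term use

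*Protocol*

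**What the plan says.** Section 7 (Rationale and background) gives LMWH a starting role: "Low-molecular-weight heparin (LMWH) is the standard initial treatment for cancer-associated VTE (CAT". The next sentence names warfarin as the recommended long-term treatment for several cancers, prostate among them.

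Section 9.3.2 lists the LMWH class as "LMWH (after hospital discharge, long-term use". The same section equates any anticoagulant filled on an out-patient prescription with long-term therapy, and says that drugs given in hospital are not recorded.

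The exposure rules are these:
- Start (9.4.1): "A start date will be defined as the date of the dispensed prescription for patients receiving anticoagulation".
- Switch (9.4.2): "A therapeutic switch will be defined as a subsequent filling of a prescription for an alternative anticoagulant (LMWH, any NOAC, VKA".
- Censoring (9.4.1): "patients who switched will be censored at the time of the date of a filled prescription from a pharmacy of the new drug".
- End of exposure (9.4.3): "the date for dispensing of the other drug was considered to mark the end of the exposure to the study drug".

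Section 9.8 then reports type and duration of anticoagulation (Objective 4), and rates of recurrent VTE, bleeding and death by type and duration (Objectives 5 and 7). The duration categories are up to 3 months, 3–6 months and more than 6 months. No comparison between classes is planned.

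**The concern.** Section 7 describes LMWH first and a VKA later as the parts of one course of treatment. Section 9.3.2 wants only the long-term use of LMWH in the LMWH class. The operational rules have no means of telling the two uses apart: no minimum time on LMWH, no overlap or bridging exception, no landmark.

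A man who fills LMWH at a pharmacy and then the planned VKA is therefore recorded as a long-term LMWH user who switched early. Objective 4 would report more LMWH as drug of choice, more short LMWH courses and more switching than the treatment plans contained. Section 7 names treatment duration and switching among the gaps that real-life data should fill, so these are figures the study exists to produce. In Objectives 5 and 7, days in the initial phase after the VTE would be pooled with long-term LMWH days under one class label.

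**Working it through.** **Tracing the rules for one man.** Suppose he fills LMWH on day 0 and warfarin on day 10.
1. 9.3.2: the LMWH fill is an out-patient fill, so it is long-term therapy.
2. 9.4.1: LMWH exposure starts on day 0.
3. 9.4.2: the warfarin fill on day 10 is a fill of an alternative class, so it is a switch.
4. 9.4.1 and 9.4.3: he is censored, and LMWH exposure ends, on day 10.
5. 9.8: his LMWH duration is in the up-to-3-months category.

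The 90-day grace period in 9.4.1 defines a new prescription; it does not alter steps 3 and 4.

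**Size.** The protocol gives no switching proportion, LMWH share or class-specific rate, so there is no stated figure to reproduce. Everything below rests on assumed inputs:
- q = share of treated men truly on long-term LMWH: 10–40%
- s = share of oral users with a pharmacy-filled LMWH lead-in: 10–60%
- true switching = 0, and class set by first fill

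Formulas:
- men classed as LMWH starters = q + (1 − q)s
- lead-in share of LMWH starters = (1 − q)s / [q + (1 − q)s]
- false switches among treated men = (1 − q)s

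| q | s | LMWH starters | Lead-in share of them | False switches |
|---|---|---|---|---|
| 40% | 10% | 0.40 + 0.06 = 46% | 0.06/0.46 = 13% | 6% |
| 20% | 10% | 0.20 + 0.08 = 28% | 0.08/0.28 = 29% | 8% |
| 20% | 30% | 0.20 + 0.24 = 44% | 0.24/0.44 = 55% | 24% |
| 20% | 60% | 0.20 + 0.48 = 68% | 0.48/0.68 = 71% | 48% |
| 10% | 60% | 0.10 + 0.54 = 64% | 0.54/0.64 = 84% | 54% |

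With s = 0 (every lead-in given in hospital) both effects are zero.

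**On-treatment person-time, all LMWH durations pooled.** Further assumptions: a lead-in of d = 7–30 days, and true LMWH use of 180 days. Lead-in share of LMWH time = (1 − q)s·d / [(1 − q)s·d + 180q].
- Low end (q = 40%, s = 10%, d = 7): 0.42/(0.42 + 72) = 0.6%.
- High end (q = 10%, s = 60%, d = 30): 16.2/(16.2 + 18) = 47%.

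Suppose also that the event rate in the first 30 days is 3 times the later rate. In units of the later rate, true long-term LMWH users then have a mean rate of (30×3 + 150)/180 = 1.333. The pooled LMWH rate is [240q + 3(1 − q)s·d] / [180q + (1 − q)s·d].
- Low end: 97.26/72.42 = 1.343, which is 0.7% above 1.333.
- High end: 72.6/34.2 = 2.123, which is 59% above 1.333.

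**The case against.** **Lead-ins given in hospital cannot be misclassified.** They are not in the data (9.3.2, 9.10). This stands, and it limits the point to pharmacy-dispensed lead-ins. It does not remove the point: 9.5 identifies VTE from out-patient as well as in-patient records, and a lead-in may continue after discharge.

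**The lead-in days are real LMWH exposure.** Counting them as LMWH and stopping at the oral fill is ordinary as-treated allocation. This also stands. A reader might infer that the on-treatment rates assign events to the wrong drug; the text does not support that. What is wrong is the long-term label and the mixing of two phases under it.

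**The duration categories contain the harm.** Short lead-ins fall in the up-to-3-months LMWH stratum, and the on-treatment strata for longer LMWH use stay clear of them. This is correct, so the pooled rate figures above would not apply to those strata. The up-to-3-months stratum and the overall LMWH and switching proportions remain affected.

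**The effect on Objectives 5 and 7 is not fully fixed by the text.** Section 9.8 runs time at risk from the VTE to event, death or end of follow-up without mentioning censoring at a switch. Nor does the protocol say that class is set by first fill. It would be tempting to conclude that the analysis ignoring current drug assigns later events in oral users to LMWH. That follows only if class is set by first fill.

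**A bridging window is analysis-plan detail.** It often is, and the analysis plan is not at hand. But this protocol does not defer the matter: it fixes the switch definition, the censoring date and the end of exposure. A bridging exception would change a stated rule.

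**Conclusion.** The passages conflict, and the stated rules followed exactly report a pharmacy-dispensed LMWH-to-VKA initiation as short LMWH therapy plus a switch. The distortion is clearest in Objective 4. In Objectives 5 and 7 it is a mixing of initial-phase and long-term LMWH, chiefly in the up-to-3-months stratum. The protocol should be changed, although the harm is confined to descriptive figures.

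The size cannot be taken from the document. The ranges of 13–84% of the LMWH stratum and 6–54% of treated men depend wholly on the assumed q and s, with zero as the floor.

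A reader might go further and take a dispensed LMWH lead-in before a VKA or a NOAC to be the usual course, and so expect a large error. The protocol does not support this. It does not say that the initial LMWH is dispensed by a pharmacy, and it describes no LMWH lead-in before a NOAC. The LMWH-to-VKA sequence in section 7 is enough to carry the point.

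**What to change.** Reconcile sections 7, 9.3.2 and 9.4.1–9.4.3 with one analytic definition; it concerns classification only and implies nothing about how patients should be treated.

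1. State in 9.4.2 that an oral anticoagulant fill within a prespecified window after the first LMWH fill is initiation of oral long-term therapy, not a switch. A window of 30 days, with 14 and 45 days as sensitivity analyses, would serve as an example.
2. Report person-time and events in the initial window as a separate initial-phase category for all classes. For men who start directly on an oral drug, count the window from their first anticoagulant fill.
3. Start long-term class-specific time at the window end for every man, classed by the drug in use then. A common landmark avoids immortal time. It also avoids the unequal early risk that would arise if oral time began at the oral fill and LMWH-only time began at the window end.

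The cost is one definition, one extra reporting category and a small sensitivity table, all on data already planned. The downsides are that a few genuine early switches will be counted as initiation, and that early events appear only in the initial-phase category. The window length is a judgement, hence the sensitivity values.

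### Any later fill of another anticoagulant counts as a switch (Protocol 9.4.2), so a first drug that is still being refilled is cut short in the on-treatment, duration and switching results

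*Protocol*

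**What the plan says.** Three parts of section 9.4 of the Protocol act together.

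- **9.4.2 Switching:** "A therapeutic switch will be defined as a subsequent filling of a prescription for an alternative anticoagulant (LMWH, any NOAC, VKA". There is no condition that the first drug has stopped, no minimum number of fills of the new drug and no allowance for overlap.
- **9.4.1 Exposure to anticoagulants:** "patients who switched will be censored at the time of the date of a filled prescription from a pharmacy of the new drug".
- **9.4.3 Discontinuation:** the end of exposure cannot be dated exactly unless there was a switch. In that case "the date for dispensing of the other drug was considered to mark the end of the exposure to the study drug".

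Without a switch, 9.4.3 approximates the end of exposure. "The refill interval method counts all days between two dispensings as days on treatment", and after a gap of more than six months, a single prescription or no further refill, "treatment will be considered to have ceased three months after the last recorded dispensing".

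Section 9.4.1 has two exposure definitions: "the first is by following the patients until the end of the follow-up time, regardless if they are still on the drug or not", and an on-treatment definition. Section 9.8 reports type and duration of treatment (up to 3 months, 3-6 months, more than 6 months) under Objective 4. It uses both as strata for the rates of recurrent VTE, bleeding and death.

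**The concern.** A switch date marks the end of the first drug only if the first drug did end. When VKA is refilled after a single LMWH fill, the dispensing record itself shows that VKA continued, and the written rule ignores those refills. Section 7 names LMWH as standard initial treatment and a VKA as long-term treatment, so fills of both classes in one man are foreseeable.

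Three results are at stake:

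- the first-drug duration under Objective 4, where one fill can move a man into a shorter stratum;
- the proportion who switch;
- the person-time and events in the on-treatment rates, which stop at the overlapping fill.

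The point concerns a first drug that continues. An LMWH fill before the first VKA fill does not shorten the VKA course.

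**Working it through.** The Protocol gives no figure that depends on this rule, so there is nothing to reproduce. I applied the written rules to one assumed fill history and then to an assumed population.

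**1. One man.** Assume VKA fills on days 0, 90, 180 and 270, and one LMWH fill. Take 3 months as 91 days and 6 months as 182 days.

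Without the switch rule, VKA ends three months after the last fill: 270 + 91 = day 361, in the stratum above 6 months. Under 9.4.2 it ends on the LMWH fill date:

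| LMWH fill (day) | Stratum assigned | Days lost | Share of 361 days | VKA fills afterwards |
|---|---|---|---|---|
| 5 | up to 3 months | 356 | 98.6% | 90, 180, 270 |
| 60 | up to 3 months | 301 | 83.4% | 90, 180, 270 |
| 100 | 3-6 months | 261 | 72.3% | 180, 270 |
| 150 | 3-6 months | 211 | 58.4% | 180, 270 |
| 200 | more than 6 months | 161 | 44.6% | 270 |
| 300 | more than 6 months | 61 | 16.9% | none |

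In every row but the last, later fills show that VKA went on.

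**2. A population.** Assumptions, none from the documents: true VKA course T uniform on 3-18 months; a share b of men has one overlap fill at time U·T, with U uniform on (0, 1).

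- Mean share of a course lost by an affected man: 1 - E(U) = 1/2. Overall person-time loss = b/2.
- True share above 6 months: (18 - 6)/15 = 80%.
- Share above 6 months among affected men: (1/15)·∫ from 6 to 18 of (1 - 6/t) dt = (12 - 6·ln 3)/15 = 0.361.
- Observed share above 6 months: 0.80 - b·(0.80 - 0.361).

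| b | Person-time loss | Share above 6 months |
|---|---|---|
| 5% | 2.5% | 77.8% |
| 10% | 5.0% | 75.6% |
| 20% | 10.0% | 71.2% |

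Under these assumptions the proportion switching from VKA to LMWH is overstated by b.

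**3. Where the rule reaches.** The on-treatment definition, treatment duration and switching all depend on the switch date. The definition that follows men whether or not they remain on the drug should not, although 9.4.1 does not say which definition its censoring list serves. Section 9.8 ends time at risk for Objectives 5-7 at event, death or end of follow-up, without naming switching.

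**The case against.** **The rules do not conflict.** A reader might infer that 9.4.2 contradicts the refill interval method, which would count the same months as continuous VKA. The text does not support that. Section 9.4.3 makes the switch date an explicit exception to its approximation methods, so the order of precedence is clear. This objection stands. What remains is that the rule, applied as written, gives a wrong duration.

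**The pattern of error is not documented.** A reader might also infer that overlap falls mainly on VKA users, or marks men having procedures, so that the error differs by class and the censoring is informative. No section says so. Drugs given in hospital are not recorded (9.3.2, 9.10) and trigger no switch, which limits how often the problem arises. Section 9.8 plans no comparison of the three classes, so no planned contrast is distorted. These points stand.

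**Waiting for a later refill can bias the rates.** Suppose VKA is filled on day 90, LMWH on day 100, and the next VKA fill is due on day 180. If the man bleeds on day 140 with no further VKA fill, a rule that looks for later refills codes a switch on day 100 and drops the bleed from VKA. If he reaches day 180 event-free, those 80 days are credited to VKA. That time is then event-free by construction. The present rule avoids this because it uses only what is known on the fill date. The objection is sound, and the fix must treat duration and event rates differently.

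**This is SAP detail.** Overlap allowances are often left to an SAP. Here, however, the Protocol itself fixes a rule, and that rule takes no account of contrary refills.

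**Conclusion.** The point holds in limited form. As written, 9.4.1 to 9.4.3 end the first drug at any fill of an alternative anticoagulant, even when later refills show that it continued. Affected men get a first-drug duration that is too short, are counted as switchers, and lose on-treatment person-time and events.

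The size cannot be derived from the documents. The loss of 2.5-10% of VKA on-treatment person-time, and the fall from 80% to about 78-71% above 6 months, rest wholly on the assumed b, course lengths and timing of the overlap. The harm is a distorted description. It should be corrected before the exposure program is fixed.

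**What to change.** Separate the two uses of the switch date.

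**(a) Duration and switching (Objective 4).** In 9.4.2, count a fill of another class as a switch only if the first class is not refilled within the six-month limit of 9.4.3. Report men whose first class is refilled in a separate row for concurrent dispensing.

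**(b) On-treatment event rates.** Do not use refills after the overlapping fill to decide whether the time in between counts. Let first-drug exposure run to the end of its own refill window, starting from the last first-drug fill before the overlap, and extend it as refills occur. Flag the overlapping time separately. Report the present any-fill censoring rule alongside as a sensitivity analysis.

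Taking the window in (b) as the three months that 9.4.3 allows after a last fill, the assumed history works as intended. The fills on days 90, 180 and 270 each fall inside the previous window (ending on days 91, 181 and 271), so exposure runs unbroken to day 361. In the example under the objection, the window from the day-90 fill ends on day 181, so the bleed on day 140 counts for VKA.

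The cost is a few sentences in 9.4.1 to 9.4.3 and a small program change. There are two downsides. A switch near the data lock stays provisional because later refills are unseen. After a true switch, some second-drug time is also counted as first-drug time until the window ends; the flag and the sensitivity analysis make that visible. These are rules for coding fills and imply nothing about treatment.

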9.4.3 Discontinuation

It will not possible to determine exactly when an anticoagulant drug was discontinued from dispensing data, except when a switch was made, where the date for dispensing of the other drug was considered to mark the end of the exposure to the study drug.

Therefore, two fundamentally different methods will be used to approximate the time when exposure to the anticoagulant drug ended: a dispensed quantity based-method and a method based on refill intervals, which have both been evaluated in a previous study (9).

The dispensed quantity method counts the number of days the dispensed quantity of the drug would last if taken as prescribed and without missed doses. As the dosing of SOC varies greatly over time and between individuals, and the dosage is not recorded in the registers, this method could only be used for NOACs.

The refill interval method counts all days between two dispensings as days on treatment. If there is a gap exceeding six months, a single prescription or no more refills, treatment will be considered to have ceased three months after the last recorded dispensing. If there is another refill after more than six months, another treatment period will be considered to have started.

For both methods, the number of days on treatment days will be added up and a medicine possession ratio (MPR) calculated as the proportion of days on treatment out of the total number of days at risk (time to end of follow up, death or emigration). As a further sensitivity analysis, both methods will be assessed assuming that all patients were fully compliant to treatment (MPR 100%) and allowing

for patient's forgetfulness that every tenth dose is missed (on average). In this case a dispensed quantity would last approximately 11% longer than with full compliance.

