9.10 Limitations of the research methods

The main limitation of this study is that only drugs dispensed to patients via a pharmacy are recorded. This means that anti-coagulation treatments and anti-cancer treatments delivered in-hospital are not recorded in the database. Therefore, as these patients with VTE events and cancer are at high risk of being hospitalized, we will likely be missing data on their prescribed anti-coagulation treatments during their in-hospital period. However, given that treatment for VTE is usually a minimum of three months will be captured by the ensuing out-patient treatment that includes filling of prescriptions.

Another limitation is that there are no data on height and weight or lifestyle factors such as smoking status, alcohol use.

No information on adherence to the drug treatment is available directly. Therefore, dates of starting and stopping exposure to anticoagulation medications may not be fully accurate, hence we have applied two ways of defining drug exposure to account for this.

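### The missed-dose sensitivity analysis in section 9.4.3 cannot alter the refill-interval method, so for VKA and LMWH the announced check is empty

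*Protocol*

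**What the plan says.** Protocol section 9.4.3 states that "two fundamentally different methods will be used to approximate the time when exposure to the anticoagulant drug ended".

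- **Dispensed-quantity method.** It counts how long the supply would last if taken as prescribed. Because dosing varies and is not recorded, "this method could only be used for NOACs".
- **Refill-interval method.** "The refill interval method counts all days between two dispensings as days on treatment". After a single dispensing, a last dispensing or a gap of more than six months, "treatment will be considered to have ceased three months after the last recorded dispensing". A refill after such a gap opens a new treatment period.

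The section then adds the compliance check: "As a further sensitivity analysis, both methods will be assessed assuming that all patients were fully compliant to treatment (MPR 100"%), and, as the alternative, an allowance "for patient's forgetfulness that every tenth dose is missed (on average"). The consequence is given in one sentence: "In this case a dispensed quantity would last approximately 11% longer than with full compliance".

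Section 9.10 accepts that start and stop dates may be inaccurate and answers that "we have applied two ways of defining drug exposure to account for this".

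Section 9.8 reports anticoagulation by class (LMWH, VKA, NOAC) and by duration (up to 3, 3-6, more than 6 months). It uses type and duration to stratify the rates of recurrent VTE, bleeding and death.

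**The concern.** A compliance scenario can change a duration only if the duration is computed from something that compliance affects. Days of supply are such a quantity; the calendar interval between two pharmacy visits is not. The protocol applies the scenario to both methods but describes its effect only in terms of supply.

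VKA and LMWH have only the refill-interval method in section 9.4.3. For these classes the report would show two matching sets of durations and two matching medicine possession ratios, which a reader could take as evidence that the durations are robust when nothing was varied. The assumptions that do set the end of treatment when no switch or censoring date is observed, the three-month tail and the six-month gap, would go untested. Those durations feed Objective 4 directly, and Objectives 5 and 7 through the stratified rates.

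**Working it through.** **Inputs, all from section 9.4.3 unless noted.** Missed doses: one in ten. Gap limit: six months, taken as 183 days. Tail: three months, taken as 91 days. Pack size is not given; 90 days of supply per dispensing is assumed for illustration.

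**1. The protocol's own figure.** If a fraction 0.10 of doses is missed, supply lasts 1/(1 − 0.10) = 1.111 times as long, or +11.1%. The stated figure of about 11% is reproduced.

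**2. The two rules as formulas.**

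- Dispensed quantity: days = sum of days of supply × multiplier, where the multiplier is 1 under full compliance and 1.111 with missed doses.
- Refill interval: days = sum of all intervals of at most 183 days + 91 days for each treatment period (one tail after its last dispensing). Neither quantity nor the multiplier appears.

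**3. Both rules on the same dispensing histories (full compliance → every tenth dose missed).**

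| Dispensing history | Refill interval, days | Dispensed quantity, days |
|---|---|---|
| Single dispensing | 91 → 91 | 90 → 100 |
| Two, 90 days apart | 181 → 181 | 180 → 200 |
| Three, 95 days apart | 281 → 281 | 270 → 300 |
| Three, intervals of 90 and 200 days | 272 → 272 | 270 → 300 |
| Six, 100 days apart | 591 → 591 | 540 → 600 |

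For example, the fourth row under the refill rule is 90 + 91 + 91 = 272, because the 200-day interval exceeds the gap limit and each of the two periods gets its own tail. In 20,000 simulated histories with varying numbers of fills, intervals and pack sizes, the refill-interval result changed in 0.

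**4. What this leaves by drug class in section 9.4.3.**

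| Class | Methods available | Effect of the missed-dose scenario |
|---|---|---|
| NOAC | Dispensed quantity and refill interval | +11.1% on the first, 0 on the second |
| VKA | Refill interval only | 0 |
| LMWH | Refill interval only | 0 |

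**5. Does the untested tail matter for the categories?** A man with one dispensing and no switch or censoring is assigned exactly three months (91 days) from that dispensing, which is the upper limit of the first category. With an illustrative tail of 4.5 months he has about 137 days and moves to the 3-6 month category. With 1.5 months he has about 46 days and stays in the first. Section 9.8 starts the duration clock at hospital discharge, so if the fill came some days after discharge, the same man could already lie just past the limit.

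**The case against.** The strongest reply is that section 9.4.3 is not the only source of an alternative. Section 9.4.1 defines an on-treatment exposure for each drug from the median interval between prescriptions, with a 90-day grace period. It is not limited to NOACs and does not use the three-month tail. This stands in part: a reader might infer that VKA and LMWH have no possible sensitivity analysis of duration, and the protocol does not support that. But the 9.4.1 rule is not designated as a sensitivity analysis, is not reconciled with the six-month and three-month constants, and contains no missed-dose term. The other 9.4.1 definition, follow-up to the end regardless of treatment, varies follow-up and not treatment duration.

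It can also be said that the tail might be stretched by 11% (91 to 101.1 days), with the detail left to an analysis plan. The protocol gives the tail as three months without qualification, and it positively prescribes the check for both methods. The issue is a stated analysis that does not work, not a missing detail.

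Three further inferences are tempting and do not hold:

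- *The shortest category can contain only men with a single fill.* Switching ends exposure at the new drug's dispensing, and section 9.4.1 also censors at events, death and end of observation. LMWH fills on days 0 and 30 with a VKA fill on day 60 give two fills and 60 days. For such men neither the tail nor the gap sets the end date.
- *A shorter tail would move single-fill men across the limit.* At about 46 days they remain in the up-to-3-month category; only a longer tail moves them.
- *Refill duration is simply last fill minus first fill plus three months.* For the fourth history that would give 290 + 91 = 381 days, against 272 under the gap rule.

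Finally, the study is descriptive and plans no comparison between anticoagulant classes. That limits the consequence but does not make the check informative.

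**Conclusion.** The point holds for the check announced in section 9.4.3. As written, the missed-dose scenario changes refill-interval durations by exactly 0 days and dispensed-quantity durations by +11.1%. For VKA and LMWH it is therefore empty and should not be presented as evidence of robustness. This follows from the definitions and needs no data; the pack size and day counts in the working are illustrative only.

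It rests on two readings. The tail is fixed at three months, as stated. LMWH falls outside the dispensed-quantity method because that method is reserved for NOACs; the reason given there refers to SOC, an abbreviation the protocol does not define.

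The consequence for the duration categories is confined to men whose treatment end is not observed through a switch or censoring. The protocol gives no count of such men, so the number who would change category cannot be stated. The correction is worth making because duration is a primary descriptive result and a stratifier of the outcome rates.

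**What to change.** In section 9.4.3, limit the 11% missed-dose scenario to the dispensed-quantity method for NOACs.

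For the refill-interval method, in all three classes, do one or both of the following:

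- vary the two analysis constants, tail and gap, with one shorter and one longer value of each fixed before the analysis;
- reconcile the section 9.4.1 median-interval rule (90-day grace period) with 9.4.3 and name it as the alternative definition of duration.

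Report the duration categories and the class-specific rates of recurrent VTE, bleeding and death under each definition. These are constants of the exposure algorithm and do not touch patient management. The cost is one changed sentence, a short addition and a few re-runs of the algorithm; no new data are needed.
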